6.6.3. Serious adverse events

The frequency (number and percentage) of participants with each of the following will be presented for treatment-emergent SAEs by treatment group:

- SAEs by SOC and PT

- Related SAEs by SOC and PT

The listings of all SAEs will also be provided with the relevant information with a flag for SAEs with onset outside of the on-treatment period.

6.6.4. Other significant adverse events

The frequency (number and percentage) of participants with each of the following will be presented for irAEs, by treatment group:

- irAEs leading to death, by Cluster and PT
- irAEs, by Cluster and PT
- irAEs, Grade ≥ 3 , by Cluster and PT
- irAEs leading to discontinuation of sasanlimab, by Cluster and PT
- irAEs leading to discontinuation of all study drugs, by Cluster and PT
- Serious irAEs, by Cluster and PT

The listing of all irAEs will also be provided with the relevant information with a flag for irAEs with onset outside of the on-treatment period.

6.6.5. Laboratory data

6.6.5.1. Hematology and chemistry parameters

Laboratory results will be classified according to the NCI-CTCAE criteria version 5.0. Non-numerical qualifiers (with the exception of fasting flags) will not be taken into consideration in the derivation of CTCAE criteria (e.g., hypokalemia Grade 1 and Grade 2 are only distinguished by a non-numerical qualifier and therefore Grade 2 will not be derived). Additional laboratory results that are not part of NCI-CTCAE will be presented according to the categories: below normal limit, within normal limits and above normal limit (according to the laboratory normal ranges).

Abnormalities classified according to NCI-CTCAE toxicity grading v.5.0 will be described using the worst grade. For those parameters which are graded with two toxicities such as potassium (hypokalemia/hyperkalemia), the toxicities will be summarized separately. Low direction toxicity (e.g., hypokalemia) grades at baseline and post baseline will be set to 0 when the variables are derived for summarizing high direction toxicity (e.g., hyperkalemia), and vice versa.

For **WBC differential counts** (total neutrophil [including bands], lymphocyte, monocyte, eosinophil, and basophil counts), the absolute value will be used when reported. When only percentages are available (this is mainly important for neutrophils and lymphocytes, because the CTCAE grading is based on the absolute counts), the absolute value is derived as follows:

$$\text{Derived differential absolute count} = (\text{WBC count}) \times (\text{Differential \%value} / 100)$$

If the range for the differential absolute count is not available (only range for value in % is available) then Grade 1 will be attributed to as follows:

- Lymphocyte count decreased:
 - derived absolute count does not meet Grade 2-4 criteria, and
 - % value < % LLN value, and
 - derived absolute count $\geq 800/\text{mm}^3$
- Neutrophil count decreased
 - derived absolute count does not meet Grade 2-4 criteria, and
 - % value < % LLN value, and
 - derived absolute count $\geq 1500/\text{mm}^3$

For **calcium**, CTCAE grading is based on Corrected Calcium and Ionized Calcium (CALCIO). Corrected Calcium is calculated from Albumin and Calcium as follows

Corrected calcium (mmol/L) = measured total calcium (mmol/L) + 0.02 (40 - serum albumin [g/L])

Liver function tests: Alanine aminotransferase (ALT), aspartate aminotransferase (AST), and total bilirubin (TBILI) are used to assess possible drug induced liver toxicity. The ratios of test result over upper limit of normal (ULN) will be calculated and classified for these three parameters during the on-treatment period.

Summary of liver function tests will include the following categories. The number and percentage of participants with each of the following during the on-treatment period will be summarized by treatment group:

- $\text{ALT} \geq 3 \times \text{ULN}$, $\text{ALT} \geq 5 \times \text{ULN}$, $\text{ALT} \geq 10 \times \text{ULN}$, $\text{ALT} \geq 20 \times \text{ULN}$
- $\text{AST} \geq 3 \times \text{ULN}$, $\text{AST} \geq 5 \times \text{ULN}$, $\text{AST} \geq 10 \times \text{ULN}$, $\text{AST} \geq 20 \times \text{ULN}$
- $(\text{ALT or AST}) \geq 3 \times \text{ULN}$, $(\text{ALT or AST}) \geq 5 \times \text{ULN}$, $(\text{ALT or AST}) \geq 10 \times \text{ULN}$, $(\text{ALT or AST}) \geq 20 \times \text{ULN}$
- $\text{TBILI} \geq 2 \times \text{ULN}$
- Concurrent $\text{ALT} \geq 3 \times \text{ULN}$ and $\text{TBILI} \geq 2 \times \text{ULN}$
- Concurrent $\text{AST} \geq 3 \times \text{ULN}$ and $\text{TBILI} \geq 2 \times \text{ULN}$
- Concurrent $(\text{ALT or AST}) \geq 3 \times \text{ULN}$ and $\text{TBILI} \geq 2 \times \text{ULN}$
- Concurrent $(\text{ALT or AST}) \geq 3 \times \text{ULN}$ and $\text{TBILI} \geq 2 \times \text{ULN}$ and $\text{ALP} > 2 \times \text{ULN}$
- Concurrent $(\text{ALT or AST}) \geq 3 \times \text{ULN}$ and $\text{TBILI} \geq 2 \times \text{ULN}$ and $(\text{ALP} \leq 2 \times \text{ULN}$ or missing)

Concurrent measurements are those occurring on the same date.

Categories will be cumulative, i.e., a participant with an elevation of AST $\geq 10 \times \text{ULN}$ will also appear in the categories $\geq 5 \times \text{ULN}$ and $\geq 3 \times \text{ULN}$. Liver function elevation and possible Hy's Law cases will be summarized using frequency counts and percentages.

An evaluation of Drug-Induced Serious Hepatotoxicity (eDISH) plot will also be created, with different symbols for different treatment groups, by graphically displaying

- peak serum ALT(/ULN) vs peak total bilirubin (/ULN) including reference lines at ALT=3×ULN and total bilirubin =2×ULN.
- peak serum AST(/ULN) vs peak total bilirubin (/ULN) including reference lines at AST=3×ULN and total bilirubin =2×ULN .

In addition, a listing of all TBILI, ALT, AST and ALP values for participants with concurrent (ALT or AST) $\geq 3 \times \text{ULN}$ and TBILI $\geq 2 \times \text{ULN}$ and (ALP $\leq 2 \times \text{ULN}$ or missing) will be provided.

Parameters with NCI-CTC grades available:

The laboratory toxicities will be tabulated using descriptive statistics (number of participants and percentages) during the on-treatment period. The denominator to calculate percentages for each laboratory parameter is the number of participants evaluable for CTCAE grading (ie those participants for whom a Grade 0, 1, 2, 3 or 4 can be derived).

- The shift table will summarize baseline CTCAE grade versus the worst on-treatment CTCAE grade. The highest CTCAE grade during the on-treatment period is considered as the worst grade for the summary.
- The number and percentage of participants with newly occurring or worsening laboratory abnormalities during the on-treatment period will be summarized by worst grade on-treatment (Grade 1, 2, 3, 4, Grade 3/4 and any grade [Grades 1-4]).

The above analyses apply to hematology and chemistry evaluations which can be graded per CTCAE.

Parameters with NCI-CTC grades not available:

Hematology and chemistry evaluations which cannot be graded per CTCAE criteria will be summarized as frequency (number and percentage) of participants with:

- shifts from baseline normal to at least one result above normal during on-treatment period
- shifts from baseline normal to at least one result below normal during on-treatment period

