5.2.7. Definition of on-treatment period

Safety endpoints will be summarized based on the on-treatment period unless otherwise specified.

On-treatment period is defined as the time from the first dose of study treatment through minimum (30 days + last dose of study treatment, start day of new anti-cancer drug therapy – 1 day).

Safety data collected outside the on-treatment period as described above will be listed and flagged in listings but not summarized.

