6.6.5.2. Other laboratory parameters

The listings of laboratory results will be provided for all laboratory parameters. The listings will be sorted by parameters and assessment dates or visits for each participant. Laboratory values that are outside the normal range will also be flagged in the data listings, along with corresponding normal ranges. A listing of CTCAE grading will also be generated for those laboratory tests.

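### Possible Hy's Law cases are counted and listed only on a same-date match, while the eDISH plots use peaks on any date; one extra row and a wider listing would bring them into line

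*SAP*

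**What the plan says.** The liver part of SAP section 6.6.5.1 has four relevant outputs.

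- **Single-parameter rows.** Counts of participants at or above set multiples of ULN for ALT, AST, either of the two, and total bilirubin. The ratios are "calculated and classified for these three parameters during the on-treatment period".
- **Five combined rows.** ALT with bilirubin, AST with bilirubin, either enzyme with bilirubin, and the last of these split by ALP (>2×ULN, or ≤2×ULN or missing). The limits are 3×ULN for the enzymes and 2×ULN for bilirubin. Every row carries the word concurrent, which is then defined: "Concurrent measurements are those occurring on the same date".
- **Two eDISH plots.** One shows "peak serum ALT(/ULN) vs peak total bilirubin (/ULN) including reference lines at ALT=3×ULN and total bilirubin =2×ULN", the other "peak serum AST(/ULN) vs peak total bilirubin (/ULN) including reference lines at AST=3×ULN and total bilirubin =2×ULN". No condition ties the dates of the two peaks together.
- **A dedicated listing.** It is described as "a listing of all TBILI, ALT, AST and ALP values for participants with concurrent (ALT or AST" and so on, again on the concurrent criterion, and is further limited to ALP ≤2×ULN or missing.

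The section also states that possible Hy's "Law cases will be summarized using frequency counts and percentages". It gives no rule for identifying such a case other than the concurrent rows. Section 6.6.5.2 adds a general listing of all laboratory results: "The listings will be sorted by parameters and assessment dates or visits for each participant". Section 5.2.7 sets the default period: "Safety endpoints will be summarized based on the on-treatment period unless otherwise specified".

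**The concern.** The same pair of limits selects two different sets of participants, depending on whether one reads the table or the plot. Enzymes may already be falling when bilirubin rises, or the two tests may be drawn a day apart. Either is enough for a participant to cross both limits without doing so on one date.

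Such a participant is a visible symbol in the upper-right part of a plot. A reader who looks for the matching case may find a combined count of zero and no entry in the dedicated listing giving dates and ALP. Because the same-date rows are the only rule in the SAP that produces a count of possible Hy's Law cases, that count would under-identify the main combined liver signal.

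The groups are small, so one participant is noticeable: 1/62 = 1.6% of Sub-Study A Phase 2, 1/20 = 5% of a Sub-Study B Phase 2 arm, and between 1/6 = 17% and 1/3 = 33% of a Sub-Study A Phase 1b cohort of 3 to 6.

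**Working it through.** The SAP states no figure to reproduce. The check applies its rules to constructed participants. All laboratory values below are assumed for illustration; only the limits and rules come from section 6.6.5.1.

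**Rules**

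- Combined row: there is a date t with ALT(t) or AST(t) ≥3×ULN and TBILI(t) ≥2×ULN (plus the ALP condition where the row has one).
- Dedicated listing: as above, with ALP ≤2×ULN or missing.
- eDISH upper-right quadrant: max over t of ALT(t) (or of AST(t)) ≥3×ULN, and max over t of TBILI(t) ≥2×ULN.

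**One participant in full.** Day 29: ALT 6.0×, TBILI 1.2×. Day 36: ALT 2.5×, TBILI 2.6×. ALP is 1.0× on both days, and AST is not raised.

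- Day 29 fails on bilirubin (1.2 < 2).
- Day 36 fails on ALT (2.5 < 3).
- Combined rows: 0 of 5. Dedicated listing: no.
- Peak pair: (6.0, 2.6), above both lines of the ALT plot.

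**Seven patterns.** The gap is the day of the bilirubin elevation minus the day of the enzyme elevation.

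| Pattern | Combined rows met | Listed | Peak rule | Gap (days) |
|---|---|---|---|---|
| A: ALT 6× and TBILI 3× same date, ALP 1× | 3 of 5 | yes | yes | 0 |
| B: ALT 10× day 1; ALT 2.5× and TBILI 3× day 8 | 0 of 5 | no | yes | +7 |
| C: ALT 10× day 1; TBILI 3× alone day 2 | 0 of 5 | no | yes | +1 |
| D: ALT 10× day 1; ALT 1× and TBILI 3× day 121 | 0 of 5 | no | yes | +120 |
| E: TBILI 3× day 1; ALT 10× day 2 | 0 of 5 | no | yes | −1 |
| F: as A, but ALP 3× | 3 of 5 | no | yes | 0 |
| G: AST 5× day 1; AST 2× and TBILI 3× day 8; ALT 1× throughout | 0 of 5 | no | yes (AST plot only) | +7 |

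The five different-date patterns (B, C, D, E, G) are in no combined row and not in the listing, and all five meet the peak rule. Pattern F is missing from the listing because of the ALP condition, not because of dates. A window of 0 to 30 days after the enzyme elevation would still miss D and E.

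**Can the other outputs recover the count?**

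- The single-parameter rows are group totals. With a participants at ALT or AST ≥3×ULN and b at TBILI ≥2×ULN among n, these rows alone fix the number with both only to the range max(0, a+b−n) to min(a, b).
- The plots show the joint classification for each enzyme, but state no count, dates or ALP. A participant can appear in the upper-right quadrant of both plots, so adding the two quadrant counts can overstate the number with either enzyme raised.
- The general listing in section 6.6.5.2 holds every value, but is sorted by parameter and selects nobody on the combined criterion.

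**The case against.** The strongest reply is that the plan pairs a specific screen (same date) with a sensitive one (peaks on any date), and that the two complement each other. The participants in question are not hidden: they appear in the plots, in the single-parameter rows and in the general listing. In groups of 20 to about 62, symbols in a quadrant can usually be counted by eye. The protocol, which is not at hand, may define potential Hy's Law cases for safety reporting. If ALT and bilirubin are always drawn together (an assumption, since the SAP gives no schedule), a miss also requires that no single draw meets both limits. Finally, a peak rule is less specific: it would count pattern D, where the enzyme is back to 1×ULN when bilirubin rises 120 days later.

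Much of this stands. The values are available, the same-date rule is a legitimate choice, and the seven patterns show how the rules behave, not how often a mismatch occurs. Two parts do not carry through. A symbol on a plot gives neither a tabulated count nor the dates and ALP needed to judge the case, and the general listing has to be searched by hand. A protocol definition for safety reporting would not change what these SAP tables count. The loss of specificity is real, but the proposal leaves the same-date rows in place and flags which cases they cover.

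**Conclusion.** The point holds as an optional, inexpensive improvement, not as an error. By construction, a participant who meets the two limits only on different dates is in 0 of 5 combined rows and not in the dedicated listing, yet above both lines of at least 1 of the 2 eDISH plots. The number of participants affected cannot be derived from the SAP. The output is descriptive, and no primary endpoint or dosing rule uses it.

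The conclusion rests on two readings. The plotted peaks carry no date link, because none is stated. They are also limited to the on-treatment period, which the SAP states for the ratios and sets as the default for safety summaries in section 5.2.7.

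**What to change.** In section 6.6.5.1:

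1. Keep the five same-date rows as they are.
2. Add one row: participants whose on-treatment peak ALT or AST is ≥3×ULN and whose on-treatment peak total bilirubin is ≥2×ULN, on any dates. This is the set of participants in the upper-right quadrant of either eDISH plot, each counted once.
3. Extend the dedicated listing to all participants in that row, whatever their ALP. Show the dates and ALP values, the number of days between the two elevations in either order, and a yes/no flag for a same-date match.
4. A row based on a time window is optional. If one is wanted, the sponsor's medical team should set its length, and it should apply in either order so that bilirubin-first cases are not lost.

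The cost is one table row, a wider listing selection and two derived columns, all from laboratory data already collected. The downside is a few extra listed participants with unrelated peaks or ALP >2×ULN, whom medical review can dismiss from the dates and values shown.

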6.6.5.2. Other laboratory parameters

The listings of laboratory results will be provided for all laboratory parameters. The listings will be sorted by parameters and assessment dates or visits for each participant. Laboratory values that are outside the normal range will also be flagged in the data listings, along with corresponding normal ranges. A listing of CTCAE grading will also be generated for those laboratory tests.

6.6.6. Electrocardiogram

QTcB and QTcF will be derived based on RR and QT (see below). The average of the replicate measurements should be determined after the derivation of the individual parameter at each time point.

Selecting Primary QT Correction for Heart Rate

The analysis of QT data is complicated by the fact that the QT interval is highly correlated with heart rate. Because of this correlation, formulas are routinely used to obtain a corrected value, denoted QTc, which is independent of heart rate. This QTc interval is intended to represent the QT interval at a standardized heart rate. Several correction formulas have been proposed in the literature. For this analysis we will use some of those methods of correction, as described below. The QT interval corrected for heart rate by the Bazett's formula, QTcB, is defined as

$$QTcB = \frac{QT}{\sqrt{RR}},$$

the QT interval corrected for heart rate by the Fridericia's formula, QTcF, is defined as

$$QTcF = \frac{QT}{\sqrt[3]{RR}},$$

where RR represents the RR interval of the ECG, in seconds, and can be estimated as 60/Heart Rate.

Although Bazett's correction is the historical standard, it does not perform well when heart rate fluctuates. Fridericia's formula may perform better under these conditions. If QTcB and QTcF methods do not adequately correct for HR and there are a sufficient number of participants (eg >30) with baseline ECGs, an alternate correction to achieve the goal of getting uncorrelated QTc and RR is based on a linear regression method which yields, theoretically, uncorrelated QTc and RR.

Linear regression method:

- Fit a model $QT = a + b \times RR$ to baseline data
- Use the estimated slope, \hat{b} , to correct QT
- Corrected QT for heart rate will be computed as follows:

$$QTcP = QT + \hat{b} \times (1 - RR)$$

Data will be summarized using QTcF and QTcB. However, if these are not appropriate for the data set due to an observed large correlation between corrected QT and HR using the baseline assessments, the results will also be summarized using QTcP.

ECG Summaries

The following analyses will be performed for each applicable ECG parameters (RR, PR, QRS, QT, ventricular rate -denoted as HR in what follows-, and QTc) by treatment group, during the on-treatment period. The denominator to calculate percentages for each category is the number of participants evaluable for the category.

- Pearson correlation between QT and HR, QTc (QTcB, QTcF and, if applicable, QTcP) and HR using individual (non-averaged) baseline assessments
- Frequency (number and percentage) of participants with notable ECG values according to the following categories:
 - QT/QTc increase from baseline >30 ms, >60 ms
 - QT/QTc > 450 ms, > 480 ms, > 500 ms
 - HR \leq 50 bpm and decrease from baseline \geq 20 bpm
 - HR \geq 120 bpm and increase from baseline \geq 20 bpm
 - PR \geq 220 ms and increase from baseline \geq 20 ms
 - QRS \geq 120 ms

Participants with notable ECG interval values and qualitative ECG abnormalities will be listed for each participant and time point and the corresponding notable values and abnormality findings will be included in the listings.

6.6.7. Physical examination

Abnormal and clinically significant physical exam findings will be reported as AEs.

7. INTERIM ANALYSES

7.1. Sub-Study A

A futility analysis based on ORR will be performed in Phase 2 to allow early termination for futility after 30 participants are treated and followed for 2 on-treatment assessments (~4 months), without holding participant enrollment. If based on the observed ORR the probability of a true ORR \geq 48% is \leq 0.10, then the study will be stopped for futility. For example, the study will be stopped for futility if \leq 10 confirmed ORs are observed in the first 30 participants treated.

The probability of stopping the sub-study (if \leq 10 confirmed ORs are observed in the first 30 participants treated) under the alternative hypothesis is 0.014.

7.2. Sub-Study B

There will be no interim analysis in Sub-Study B.

9. APPENDICES

Appendix 1. Immune-Related Adverse Events

The MedDRA PTs and clusters for irAEs are defined in the SRP for sasanlimab.

Immune-related AEs (irAEs) will be programmatically identified as outlined in Table 15. Unless otherwise noted, this case definition is hierarchical, i.e., each step is only checked for participants and events that have already met the prior step.

Table 15. Case Definition for irAEs

Step	Selection Criteria	
1	Adverse Event (AE) selected based on a list of pre-specified MedDRA PTs within clusters. These are included in the SRP. If AE matches the list, then it is included in the next step.	
2	AE onset on or after the first dose of study drug and on or before 90 days after last dose of study drug.	This is regardless of start of new anti-cancer drug therapy and regardless of TEAE classifications.
3	AE treated with corticosteroids or other immunosuppressant therapy. For endocrinopathies only: AE required hormone replacement.	Look in the conmed pages for AEs where concomitant medications match any of the following A) conmed ATC code is in (H02A, H02B, D07, A01AC, S01BA, S01BB, L04AA, L04AB, L04AC, L04AD, L04AX, A07EA) and AE PT is in any of the irAE clusters. B) conmed ATC code is in (H03A, H03B) and AE PT is in one of the irAE clusters associated with “Immune-mediated endocrinopathies” C) conmed ATC code is A10A and AE PT is in the irAE cluster associated with “Immune-mediated endocrinopathies: Type I Diabetes Mellitus”

The data set associated with irAEs may be refined based on medical review. The final data set including any changes based on medical review (e.g., addition of cases that are not selected by the programmatic algorithm) will be the basis of the irAE analyses.

Appendix 2. BLRM (Sub-Study A)

Detailed Dose Escalation/De-escalation Scheme for BLRM Design for Sasanlimab + Encorafenib + Binimetinib

This section provides the details of the statistical model, the derivation of prior distributions from historical data, the results of the Bayesian analyses and respective dosing decisions for some hypothetical data scenarios, and a simulation study of the operating characteristics of the model for the encorafenib, binimetinib, and sasanlimab triplet combination.

Statistical Model

The statistical model for combination dose-DLT data comprises single-agent toxicity parts, and interaction parts. The single-agent toxicity parts allow the incorporation of single-agent toxicity data

Single-Agent Parts

Let $\pi_1(d_1)$ be the risk of DLT for encorafenib given as a single agent at dose d_1 ; $\pi_2(d_2)$ be the risk of DLT for binimetinib given as a single agent at dose d_2 ; and $\pi_3(d_3)$ be the risk of DLT for sasanlimab given as a single agent at dose d_3 . These single agent dose-DLT models are 2 parameter logistic regression models:

$$\text{encorafenib: } \text{logit}(\pi_1(d_1)) = \log(\alpha_1) + \beta_1 \log(d_1/d_1^*)$$

$$\text{binimetinib: } \text{logit}(\pi_2(d_2)) = \log(\alpha_2) + \beta_2 \log(d_2/d_2^*)$$

$$\text{sasanlimab: } \text{logit}(\pi_3(d_3)) = \log(\alpha_3) + \beta_3 \log(d_3/d_3^*)$$

where $d_1^*=450$ mg, $d_2^*=45$ mg, and $d_3^*=300$ mg are used to scale the doses of encorafenib, binimetinib, and sasanlimab, respectively. Hence, α_1 , α_2 , and α_3 (all >0) are the single-agent odds of a DLT at d_1^* mg, d_2^* mg, and d_3^* mg, respectively; and β_1 , β_2 , and β_3 (all >0) are the increase in the log-odds of a DLT by a unit increase in log-dose.

Interaction Parts

Under an assumption that there is no interaction, the risk of a DLT at dose d_1 of encorafenib, dose d_2 of binimetinib, and dose d_3 of sasanlimab is:

$$\pi_{123}^0(d_1, d_2, d_3) = 1 - (1 - \pi_1(d_1))(1 - \pi_2(d_2))(1 - \pi_3(d_3))$$

To model the interaction between encorafenib, binimetinib, and sasanlimab, the following 4 odds multipliers are introduced.

η_{12} : 2-way interaction between encorafenib and binimetinib

η_{13} : 2-way interaction between encorafenib and sasanlimab

η_{23} : 2-way interaction between binimetinib and sasanlimab

η_{123} : 3-way interaction between encorafenib, binimetinib, and sasanlimab

The risk of DLT for combination dose (d_1, d_2, d_3) is then given by:

$$\text{odds}(\pi_{123}(d_1, d_2, d_3)) = g(\eta_{12}, \eta_{13}, \eta_{23}, \eta_{123}) \times \text{odds}(\pi_{123}^0(d_1, d_2, d_3))$$

$$\begin{aligned} g(\eta_{12}, \eta_{13}, \eta_{23}, \eta_{123}) = & \exp(\eta_{12} \times d_1/d_1^* \times d_2/d_2^*) \\ & \times \exp(\eta_{13} \times d_1/d_1^* \times d_3/d_3^*) \\ & \times \exp(\eta_{23} \times d_2/d_2^* \times d_3/d_3^*) \\ & \times \exp(\eta_{123} \times d_1/d_1^* \times d_2/d_2^* \times d_3/d_3^*) \end{aligned}$$

where $\text{odds}(\pi) = \pi/(1 - \pi)$; η_{ij} is the log-odds ratio between the interaction and no interaction model at the reference doses of drug i and j and a zero dose of the third drug. For example, η_{23} is the log-odds ratio between the interaction and no interaction model at encorafenib = 0 mg, binimetinib = 45 mg and sasanlimab = 300 mg. Therefore, $\eta_{12} + \eta_{13} + \eta_{23} + \eta_{123}$ is the log-odds ratio between the interaction and no interaction model at the reference doses for all 3 drugs. Here $\eta = 0$ corresponds to no interaction, with $\eta > 0$ and $\eta < 0$ representing synergistic and antagonistic toxicity, respectively.

Inclusion of the Doublet Data

Based on the preliminary data from the Phase 1b part of study CMEK162X2110, a total 47 participants were enrolled at the starting dose level of 45 mg for binimetinib in combination with escalating doses of encorafenib (ranging from 50 mg to 800 mg). Forty-four (44) participants were DLT-evaluable. This information from study CMEK162X2110 was incorporated in the assessment of prior distribution of DLT, starting dose, data scenarios, and simulations of triplet via a direct down-weighting approach. The weight was calculated using the formula below assuming moderate heterogeneity between the populations included in the binimetinib + encorafenib doublet and triplet in terms of DLT;

$$w = \frac{1}{1 + \frac{2\tau^2}{\sigma^2} N}$$

where, N= Total number of participants enrolled in the CMEK162X2110 (N=44)

σ = population standard deviation ($\sigma = 2$)

τ = heterogeneity between populations in the CMEK162X2110 and current trial ($\tau = 0.25$)

Prior Specifications

The Bayesian approach requires the specification of prior distributions for all model parameters, which include the single agent parameters $\log(\alpha_1)$, $\log(\beta_1)$ for encorafenib, $\log(\alpha_2)$, $\log(\beta_2)$ for binimetinib, $\log(\alpha_3)$, $\log(\beta_3)$ for sasanlimab, and the interaction parameters $\eta = (\eta_{12}, \eta_{13}, \eta_{23}, \eta_{123})$. A meta-analytic-predictive (MAP) approach was used to derive the prior distribution for the single-agent model parameters.

Prior Distribution for the Logistic Parameters for Single Agent

This section illustrates the derivation of prior distributions for single agent model parameters ($\log(\alpha_s)$, $\log(\beta_s)$)'s using the available single agent dose-DLT information via a MAP approach.

Description of the Meta-Analytic-Predictive Approach

The aim of the MAP approach is to derive a prior distribution for the logistic parameters $(\log(\alpha^*), \log(\beta^*))$ of the new trial using DLT data from historical studies. Let r_{ds} and n_{ds} be the number of participants with a DLT, and the total number of participants at dose d in historical trial s ($s = 1, \dots, \langle S \rangle$). The corresponding probability of a DLT is π_{ds} . The model specifications are as follows:

$$r_{ds} \mid \pi_{ds} \sim \text{Binomial}(\pi_{ds}, n_{ds})$$

$$\text{logit}(\pi_{ds}) = \log(\alpha_s) + \beta_s \log(d/d^*)$$

$$(\log(\alpha_s), \log(\beta_s)) \mid \mu, \psi_{g(s)} \sim \text{Bivariate Normal (BVN)}(\mu, \psi_{g(s)}), \quad s = 1, \dots, \langle S \rangle$$

$$(\log(\alpha^*), \log(\beta^*)) \mid \mu, \psi_{g(*)} \sim \text{BVN}(\mu, \psi_{g(*)})$$

The historical trials are partitioned into $\langle G \rangle$ exchangeability groups, with the exchangeability group membership of historical trial s being represented by $g(s)$. The new trial is assigned to exchangeability group $g(*)$. The parameter $\mu = (\mu_1, \mu_2)$ is the mean for the logistic parameters, and ψ_g is the between-trial covariance matrix for exchangeability group $g = 1, \dots, \langle G \rangle$. Covariance matrix ψ_g is defined by the standard deviations (t_{g1}, t_{g2}) , and correlation r (a common value for r is used across all groups). The parameters t_{g1} and t_{g2} quantify the degree of between trial heterogeneity for exchangeability group g . With different prior distributions for the parameter sets (t_{g1}, t_{g2}) it is possible to allow for differential discounting for the historical strata. In this way the quality and relevance of historical data can be accounted for in the meta-analysis. The following priors will be used for these parameters:

- normal priors for μ_1 and μ_2 ,
- log-normal priors for t_{g1} and t_{g2} , and
- uniform prior for r .

The MAP prior for single-agent model parameters in the new trial, $(\log(\alpha^*), \log(\beta^*))$, is the predictive distribution

$$(\log(\alpha^*), \log(\beta^*)) \mid (r_{ds}, n_{ds} : s = 1, \dots, \langle S \rangle)$$

Since the predictive distribution is not available analytically, the Markov chain Monte Carlo (MCMC) method is used to simulate values from this distribution. This is implemented using Just Another Gibbs Sampler (JAGS) version 4.8.

Single-Agent Encorafenib

Dose-DLT data from the encorafenib IB (Edition 10) from Study CLGX818X2101 as presented in Table 16 are used to derive the prior of the single agent logistic parameters for encorafenib.

Table 16. Historical Dose Limiting Toxicity data from study CLGX818X2101

Encorafenib Dose (mg; QD)	Number of Participants	Number of Participants with DLTs
50	4	0
100	9	1
150	6	0
200	3	0
300	5 (escalation); 14 (expansion)	1(escalation); 2 (expansion)
450	6 (escalation); 27 (expansion)	0 (escalation); 9(expansion)
550	4	1
700	2	2

Weakly informative normal priors are assumed for μ_{1e} and μ_{2e} , with means corresponding to a 50% chance of DLT at encorafenib = 450 mg and a doubling in dose leading to a doubling in the odds of the risk of a DLT, respectively. Priors for t_{1e} and t_{2te} are assigned such that (1) their medians correspond to moderate to large between trial heterogeneity, and (2) their uncertainty (95% prior interval) cover plausible between-trial standard deviations (Table 17).⁸

Table 17. Prior Distributions for the Parameters of the MAP Model Used to Derive the Prior for the Single-Agent Encorafenib Model Parameters

Parameter	Prior Distribution
μ_{1e}	N (mean = 0, sd = 2)
μ_{2e}	N (mean = 0, sd = 1)
t_{1e}	log-normal (mean = log (0.50), sd = log (2)/1.96)
t_{2e}	log-normal (mean = log (0.25), sd = log (2)/1.96)
r_e	Uniform (-1,1)

Single-Agent Binimetinib

Dose-DLT data in the binimetinib IB (Edition 16) from studies ARRAY-162-111 and CMEK162X1101 as presented in Table 18 are used to derive the prior of the single agent logistic parameters for binimetinib.

Table 18. Historical Dose Limiting Toxicity Data from Study Array-162-111 and Study CMEK162X1101

Binimetinib dose (mg BID)	Study Array-162-111		Study CMEK162X1101	
	Number of Participants	Number of Participants with DLTs	Number of Participants	Number of Participants with DLTs
30	3	0	6	0
45	43	2	15	2
60	40	2		
80	3	2		

Weakly informative normal priors are assumed for μ_{1b} and μ_{2b} , with means corresponding to a 50% chance of DLT at binimetinib = 45 mg, and a doubling in dose leading to a doubling in the odds of the risk of a DLT, respectively. The priors for between-trial heterogeneity parameters are set in the following way:

- Priors for t_{11b} and t_{12b} (ARRAY-162-111) are assigned such that (1) their medians correspond to moderate between-trial heterogeneity, and (2) their uncertainty (95% prior interval) cover plausible between-trial standard deviations.
- Priors for t_{21b} and t_{22b} (CMEK162X1101) are assigned such that (1) their medians correspond to large between-trial heterogeneity, and (2) their uncertainty (95% prior interval) cover plausible between-trial standard deviations.

Study ARRAY-162-111 is a Phase 1 study conducted in advanced or metastatic cancer participants the US. Study CMEK162X1101 is a study in Japanese participants with advanced solid tumors whose disease has progressed despite standard therapy or for whom no standard therapy exists. The participant population in Study CMEK162X1101 is less similar to Study B8011011 and hence large between trial heterogeneity is assumed.

Table 19. Prior Distributions for the Parameters of the MAP Model Used to Derive the Prior for the Single-Agent Binimetinib Model Parameters

Parameter	Prior Distribution
μ_{1b}	N (mean = 0, sd = 2)
μ_{2b}	N (mean = 0, sd=1)
t_{11b}	log-normal (mean = log (0.25), sd = log (2)/1.96)
t_{12b}	log-normal (mean = log (0.125), sd = log (2)/1.96)
t_{21b}	log-normal (mean = log (1), sd = log (2)/1.96)
t_{22b}	log-normal (mean = log (0.5), sd = log (2)/1.96)
r_b	Uniform (-1,1)

(t_{11b}, t_{12b}) = the degree of between trial heterogeneity for Study ARRAY-162-111; (t_{21b}, t_{22b}) = the degree of between-trial heterogeneity for Study CMEK162X1101.

Single Agent PF-06801591

Dose-DLT data from study B8011001 presented in Table 20 are used to derive the prior of the single agent logistic parameters for sasanlimab.

Table 20. Historical Dose Limiting Toxicity data from Study B8011001

Sasanlimab Dose (mg/once per cycle)	Number of Participants	Number of Participants with DLTs
300	15	0

Weakly informative normal priors are assumed for μ_{1p} and μ_{2p} , with means corresponding to a 50% chance of DLT at sasanlimab = 300mg, and a doubling in dose leading to a doubling in the odds of the risk of a DLT, respectively. Priors for t_{1p} and t_{2p} are assigned such that (1) their medians correspond to moderate between trial heterogeneity, and (2) their uncertainty (95% prior interval) cover plausible between-trial standard deviations (Table 21).⁸

Table 21. Prior Distributions for the Parameters of the MAP Model Used to Derive the Prior for the Single-Agent Sasanlimab Model Parameters

Parameter	Prior Distribution
μ_{1p}	N (mean = 0, sd = 2)
μ_{2p}	N (mean = 0, sd=1)
t_{1p}	log-normal (mean = log (0.25), sd = log (2)/1.96)
t_{2p}	log-normal (mean = log (0.125), sd = log (2)/1.96)
r_p	Uniform (-1,1)

N=normally distributed; sd=standard deviation.

Prior Distribution for the Interaction Parameters

Normal priors for the log-odds multipliers $\eta_{12}, \eta_{13}, \eta_{23}, \eta_{123}$ are used. The prior for $\eta_{12}, \eta_{13}, \eta_{23}, \eta_{123}$ are specified as percentiles of increase in the odds of DLT due to possible interaction in combination therapy at reference doses;

η_{12} is normally distributed, with mean -0.198 and standard deviation 0.101 (corresponds to 20% decrease in DLT odds at median and no increase in DLTs at 97.5th percentile)

η_{13} is normally distributed, with mean 0 and standard deviation 0.467 (corresponds to no increase in DLT odds at median and 2.5-fold increase in DLTs at 97.5th percentile)

η_{23} is normally distributed, with mean 0 and standard deviation 0.467 (corresponds to no increase in DLT odds at median and 2.5-fold increase in DLTs at 97.5th percentile)

η_{123} is normally distributed, with mean 0 and standard deviation 0.354 (corresponds to no increase in DLT odds at median and 2-fold increase in DLTs at 97.5th percentile).

η_{12} : 2-way interaction between encorafenib and binimetinib;

η_{13} : 2-way interaction between encorafenib and sasanlimab;

η_{23} : 2-way interaction between binimetinib and sasanlimab;

η_{123} : 3-way interaction among encorafenib, binimetinib, and sasanlimab.

Summary of Prior Distributions

The prior distributions of the model parameters are provided in Table 22.

Table 22. Prior Distribution for the Model Parameters

Parameter	Mean	Standard Deviations	Correlation
Encorafenib single agent parameters: BVN MAP Prior			
$(\log(\alpha_1), \log(\beta_1))$	-0.904, 0.268	0.822, 0.630	0.117
Binimetinib single agent parameters: BVN MAP Prior			
$(\log(\alpha_2), \log(\beta_2))$	-2.785, 0.376	0.596, 0.860	-0.330
Sasanlimab single agent parameters: BVN MAP Prior			
$(\log(\alpha_3), \log(\beta_3))$	-3.247, -0.0135	1.165, 1.009	0.00001
Interaction parameters: Normal prior			
η_{12}	-0.198	0.101	
η_{13}	0	0.467	
η_{23}	0	0.467	
η_{123}	0	0.354	

η_{12} : 2-way interaction between encorafenib and binimetinib;

η_{13} : 2-way interaction between encorafenib and sasanlimab;

η_{23} : 2-way interaction between binimetinib and sasanlimab;

η_{123} : 3-way interaction between encorafenib and binimetinib and sasanlimab.

From Table 23, encorafenib = 300 mg (QD), binimetinib = 45 mg (BID), and sasanlimab = 300 mg once per cycle is an acceptable starting dose for this triple combination.

